15 SPONSORSHIP AND INSURANCE

The University of Oxford has a specialist insurance policy in place: - Newline Underwriting Management Ltd, at Lloyd's of London – which would operate in the event of any Participant suffering harm as a result of their involvement in the research.

16 PUBLICATION POLICY

Any data published in the peer-reviewed medical literature will protect the identity of the participants. This trial will be registered in a web based protocol registration scheme. All those who have made a substantial contribution will be co-authors on publications. The sites have the right to publish their data individually and to include members of the sponsor's team who have made a significant contribution. There will also publications of pooled data which will be coordinated by the MORU group. All sites will have the opportunity to contribute to these publications.

All the research findings from the programme and from relevant research outside the Programme will be analysed and integrated, and through the WHO Global Malaria Programme will be disseminated to policy makers, National Malaria Control Programmes (NMCPs) and other researchers.

18 APPENDIX 1. SCHEDULE OF ASSESSMENTS

TEST/APPLICATION	SCREENING	D0	D1	D2	CCM*	D28-35	CCM*	D56-63	CCM*	D84-91	CCM* up to D112
Informed consent	X										
Demographics		X									
Risk history		X				X		X		X	
Travel history		X				X		X		X	
Medical and drug history		X									
Symptoms questionnaire		X				X		X		X	
Temperature		X									
Weight		X									
Randomisation and assign study ID		X									
AL/multivitamin doses to be given		X	X	X							
Plasmodium PCR		X				X		X		X	
Blood for storage (serology)		X									
Plasmodium genetic analysis (DBS)					X*		X*		X*		X*

*CCM = episode of confirmed clinical malaria between enrolment and follow-up

19 APPENDIX 2. DOSING SCHEDULES**19.1 Artemether-lumefantrine**

Artemether -lumefantrine dosing schedule										
One tablet AL contains 20 mg artemether and 120 mg lumefantrine (Coartem)										
	No. of tablets recommended at approximate timing of dosing									
	Day 1		Day 2		Day 3		Day 8		Weekly	
Weight: Kilogram	0h	8h	24h	36h	48h	60h	168h	176h	336h	344h
15 - <25	2	2	2	2	2	2	2	2	2	2
25 - <35	3	3	3	3	3	3	3	3	3	3
≥35	4	4	4	4	4	4	4	4	4	4
Alternative preparation: one tablet AL contains 80 mg artemether and 480 mg lumefantrine (Artefan)										
	No. of tablets recommended at approximate timing of dosing									
	Day 1		Day 2		Day 3		Day 8		Weekly	
Weight: Kilogram	0h	8h	24h	36h	48h	60h	168h	176h	336h	344h
≥35	1	1	1	1	1	1	1	1	1	1

19.2 Multivitamin

Multivitamin dosing schedule					
One tablet contains Vitamin -A : 5000 USP units Vitamin D: 400 USP Units Ascorbic acid: 75 mg Thiamine Mononitrate: 2 mg Riboflavin: 3 mg Niacin amide: 20 mg Or suitable equivalent alternative					
	No. of tablets recommended at approximate timing of dosing				
	Day 1	Day 2	Day 3	Day 8	Weekly
Weight: Kilogram	0h	24h	48h	168h	336h ...
≥15	1	1	1	1	1

21 APPENDIX 4. AMENDMENT HISTORY

Amendment No.	Protocol Version No.	Date issued	Author(s) of changes	Details of Changes made
Not applicable

#### 1. INTRODUCTION

In the Greater Mekong Subregion (GMS) adults are at highest risk for malaria. The most relevant disease vectors bite during daytime and outdoors which makes forest work a high-risk activity for malaria. The absence of effective vector control strategies and limited periods of exposure during forest visits suggest that chemoprophylaxis could be an appropriate strategy to protect forest workers against malaria. We propose to evaluate the feasibility and protective efficacy of antimalarial prophylaxis during forest work.

The proposed study will help to assess the efficacy and feasibility of prophylaxis to prevent malaria in forest workers, help to identify the optimal regimen, and predict its efficacy in reducing overall transmission. The proposed study is a critical step for future use of chemoprophylaxis to protect forest workers in the GMS against malaria.

This document sets out the statistical analysis plan for an open-label individually randomised controlled trial to assess the efficacy of artemether-lumefantrine (AL) prophylaxis for malaria among forest goers in Cambodia.

#### 2. STUDY OBJECTIVES AND ENDPOINTS

2.1 PRIMARY OBJECTIVE

To compare the efficacy of the ACT artemether-lumefantrine versus a multivitamin preparation as defined by the 28-day **PCR parasite positivity rate or incidence of confirmed clinical malaria** of any species.

- 2.2 PRIMARY ENDPOINT
  - The 28-day PCR Plasmodium positivity rate of any species or
  - Proportion of participants with **confirmed clinical malaria** of any species reported between day 0 and day 28, at any and each of the Month 1, Month 2 or 3 follow-ups.
- 2.3 SECONDARY OBJECTIVES AND ENDPOINTS

This section outlines the secondary objectives and the corresponding endpoints. A detailed plan for analysis of some of these endpoints will be produced the specialised groups as shown below:

• To compare the efficacy of the ACT artemether-lumefantrine (AL) versus a multivitamin preparation as defined by the 28-day, 56-day and 84-day PCR parasite positivity rate or incidence of confirmed clinical malaria for each species.

Composite endpoint

- 28-day, 56-day and 84-day PCR Plasmodium positivity rate for each Plasmodium species or
- Proportion of participants with confirmed malaria reported between day 0 and day 28 for each species
- To quantify the impact of the ACT artemether-lumefantrine (AL) as prophylaxis for forest goers on overall malaria transmission using mathematical modelling.

 To assess the impact of artemether-lumefantrine prophylaxis (AL) on the spread of genetic markers of artemisinin (such as Kelch13 mutations) and partner drug resistance.
 Endpoint

- Prevalence of Kelch13 mutations and other genetic markers of antimalarial drug resistance of known functional significance

 To obtain data on the place of residence, work, recent travel history and risk behaviours of forest goers in order to improve the understanding of high risk groups, locations of malaria transmission and possible routes of spread of malaria and artemisinin resistance.
 Endpoint

- Data on the place of residence, work, recent travel history and mobile phone use events covering the whole population during the course of prophylaxis.

 To obtain detailed data and GPS mapping on a subset of participants and their peers relating to the behaviours and risk factors associated with malaria infection in order to improve understanding of local malaria transmission among forest goers.
 Endpoint

- Detailed data and GPS mapping on a subset of participants and their peers relating to the behaviours and risk factors associated with malaria infection

- To determine the prevalence of asymptomatic Plasmodium infections in high risk populations at varying seasonal time points.
   Endpoint
  - Overall prevalence of Plasmodium at baseline, stratified by season and risk factors
- 2.4 GENERAL

The study takes place at up to 50 villages in selected malaria endemic districts in Stung Treng and Pursat Provinces, Cambodia. As the malaria situation in these areas is dynamic, the villages will be identified prior to the start of the trial from analysis of up to date malaria incidence from passive surveillance collected by the Cambodia National Center for Parasitology Entomology and Malaria Control. If there are found to be insufficient villages with malaria cases in Stung Treng Province at the time of trial commencement, we will include additional sites in Pursat Province. MORU has existing study sites and teams in both provinces which will support the running of this trial. The rationale for choosing these areas include high forest cover and ongoing malaria transmission among forest goers.

#### 2.5 DETERMINATION OF SAMPLE SIZE

The target population for this study will be adult Cambodians who work and sleep in the forest (farmers, collect forest goods, hunting, etc.). 2,200 study participant episodes are required in each arm to have sufficient power to detect a statistically significant difference between the treatment arm and a control arm. The estimate of the required sample size is complicated by the scarce data on *P.falciparum* (*Pf*) incidence in forest workers. Formally, we anticipate that the risk of being Pf positive without receiving prophylaxis will be around 5%. A total of 1,605 participant-episodes per arm are enough to detect a difference of at least 40% in the proportion of episodes with a Pf positive result as defined by the 28-day PCR parasite positivity rate i.e. from 5% positivity in participants without receiving antimalarial prophylaxis (i.e. multivitamin) to 3% positivity in participants receiving artemether-lumefantrine prophylaxis. This has been estimated with 80% power and 5% significance level. However, we also anticipate that we will likely observe multiple episodes being recruited into the study that can reduce power of the study if not accounted for. To compensate for the multiple episodes and any losses to follow up, we plan to recruit approximately 600 (i.e. 595) additional episodes in each group on top of the required 1605 single episodes. This gives an additional 27% episodes to account for the multiple episodes and losses to follow up. Thus, the overall sample size will be 4,400 episodes (i.e. 2,200 episodes in the treatment arm and 2,200 episodes in the control arm). The sample size calculations have been performed in Stata version 15.

#### 3. ANALYSIS CONSIDERATIONS

3.1 GENERAL ANALYSIS APPROACH

The main analysis strategy for the primary outcome will be the intention-to-treat (ITT) principle. In this analysis, participants will be analysed according to the arm of randomisation irrespective of the treatment that was actually received.

These analyses will be followed by the per protocol (PP) analysis. In this analysis, only those that adhered to the protocol with respect to the primary outcome will be included for analysis of the primary outcome. For some objectives, data analysis will mainly be performed using Stata 16 or higher, StataCorp, 4905 Lakeway Drive College Station, Texas 77845 USA. While R or Python will be used for other endpoints. Specialised analyses such as GPS mapping, and spatial analysis will use ArcGIS 10.3 or higher, ESRI, 380 New York Street, Redlands, California USA.

#### 3.2 DATA INTEGRITY

This study will be conducted in compliance with the protocol, relevant Standard Operating Procedures (SOPs), Good Clinical Practice (GCP) and the applicable regulatory requirement(s). All the analyses will be performed on clean data only.

#### 3.3 DATA CLEANING AND VERIFICATION

All data will be cleaned and verified prior to statistical analysis. The study site will be visited by the Monitor periodically at times agreed on with the Investigator. At the time of each monitoring visit, the Monitor will review the completed CRFs to ascertain that all items have been completed and that the data provided are accurate and obtained in the manner specified in the protocol. The Monitor will also check that the data in

the CRF are consistent with the clinical records (Source Data Verification [SDV]) and that study results are recorded completely and correctly. The data manager will ensure that clean data is submitted to the statistician for analysis. The statistician will cross-check that the available data for analysis is clean. Any data cleaning queries will need to be resolved before statistical analyses.

3.4 LOCKING THE DATASET

After data cleaning and responding to all data queries, the clean data will be locked normally in the database that was used for data capturing. The data may also be locked and stored in other user-friendly formats such as MS Excel and Stata. The locked data will be stored at an identifiable secure place and should be available to the relevant researchers upon request following proper request procedures. The data will also be in other backup media such as CDs or tapes.

#### 3.5 DATA FORMAT AND ANALYSIS LOGS

Prior to dispensing data to the trial statistician, the head of data management will make sure that the data to be sent to the trial statistician is clean. This will help the statistician to provide the analysis results in a timely manner as there will be a reduced amount of queries if clean data is provided to the trial statistician. Data will be given to the Trial Statistician by the head of Data Management (or designated person) in a format that is compatible with statistical software reading. Statistical analyses will be performed in Stata, version 16 or higher. Statistical programs and output logs will be kept for all analysis and made available upon request.

#### 3.6 INTERIM ANALYSES

[figure not shown]
There was no interim analysis for this trial. Hence, no adjustment will be made to account for interim analysis of the trial efficacy differences.

#### 4. DATA ANALYSIS

#### 4.1 TRIAL PROFILE

The number of participants who will be screened, reasons for non-enrolment, number of participants randomized, number of participants lost to follow up and the number of participants assessed for 28-day endpoint will be summarised in a CONSORT flow diagram, figure 1, below.

#### Figure 1 Consort Trial Profile by Arms

#### 4.2 DEMOGRAPHICS AND OTHER BASELINE CHARACTERISTICS

The following baseline characteristics will be described by study arm in table 1 (below). Age will be summarized using median and interquartile range. Weight and tympanic temperature will be summarized using mean and standard deviation. Categorical variables such as sex and presence of symptoms at baseline will be summarized using frequencies and percentages.

### Table 1. Baseline Characteristics of the Participants

Characteristics	Artemether-Lumefantrine (N=XXX)	Multivitamin (N=XXX)	Total (N=XXX)
Demographics			
Age (years), median (IQR)	XX.X (XX.X - XX.X)	XX.X (XX.X - XX.X)	XX.X (XX.X - XX.X)
Male sex, n (%)	XX (XX.X)	XX (XX.X)	XX (XX.X)
Weight (kg), mean (SD)	XX.X (XX.X)	XX.X (XX.X)	XX.X (XX.X)
Tympanic temperature* (°C), mean (SD)	XX.X (XX.X)	XX.X (XX.X)	XX.X (XX.X)
Nationality, n (%)			
Khmer	XX (XX.X)	XX (XX.X)	XX (XX.X)
Laos	XX (XX.X)	XX (XX.X)	XX (XX.X)
Thai	XX (XX.X)	XX (XX.X)	XX (XX.X)
Others (including English)	XX (XX.X)	XX (XX.X)	XX (XX.X)
Occupation, n (%)			
Farmer	XX (XX.X)	XX (XX.X)	XX (XX.X)
Fishing	XX (XX.X)	XX (XX.X)	XX (XX.X)
Student	XX (XX.X)	XX (XX.X)	XX (XX.X)
Millitary	XX (XX.X)	XX (XX.X)	XX (XX.X)
Housewife	XX (XX.X)	XX (XX.X)	XX (XX.X)
Others	XX (XX.X)	XX (XX.X)	XX (XX.X)
Place of residence, n (%)			
Stung Treng	XX (XX.X)	XX (XX.X)	XX (XX.X)
Siem Pang	XX (XX.X)	XX (XX.X)	XX (XX.X)
Others	XX (XX.X)	XX (XX.X)	XX (XX.X)
Participants with prior malaria episodes , n (%)	XX (XX.X)	XX (XX.X)	XX (XX.X)
Symptoms, n/N (%)			
Headache	XX/XX (XX.X)	XX/XX (XX.X)	XX (XX.X)
Loss of appetite	XX/XX (XX.X)	XX/XX (XX.X)	XX (XX.X)
Dizziness	XX/XX (XX.X)	XX/XX (XX.X)	XX (XX.X)
Joint pain	XX/XX (XX.X)	XX/XX (XX.X)	XX (XX.X)
Abdominal pain	XX/XX (XX.X)	XX/XX (XX.X)	XX (XX.X)
Fatigue	XX/XX (XX.X)	XX/XX (XX.X)	XX (XX.X)
Nausea	XX/XX (XX.X)	XX/XX (XX.X)	XX (XX.X)
Vomiting	XX/XX (XX.X)	XX/XX (XX.X)	XX (XX.X)
Diarrhoea	XX/XX (XX.X)	XX/XX (XX.X)	XX (XX.X)
Itching/ rash	XX/XX (XX.X)	XX/XX (XX.X)	XX (XX.X)

Cough	XX/XX (XX.X)	XX/XX (XX.X)	XX (XX.X)
Antimalarial drug history, n			
(%)			
Drug1	XX (XX.X)	XX (XX.X)	XX (XX.X)
Drug2	XX (XX.X)	XX (XX.X)	XX (XX.X)
Drug3	XX (XX.X)	XX (XX.X)	XX (XX.X)
ect.	XX (XX.X)	XX (XX.X)	XX (XX.X)
Medical history, n (%)			
Disease1	XX (XX.X)	XX (XX.X)	XX (XX.X)
Disease2	XX (XX.X)	XX (XX.X)	XX (XX.X)
Disease3	XX (XX.X)	XX (XX.X)	XX (XX.X)
etc.	XX (XX.X)	XX (XX.X)	XX (XX.X)
Malaria history, n (%)			
Malaria1	XX (XX.X)	XX (XX.X)	XX (XX.X)
Malaria1	XX (XX.X)	XX (XX.X)	XX (XX.X)
Malaria1	XX (XX.X)	XX (XX.X)	XX (XX.X)
etc.	XX (XX.X)	XX (XX.X)	XX (XX.X)
Physical examination, n (%)			
Movement abnormality	XX (XX.X)	XX (XX.X)	XX (XX.X)
Skin abnormality	XX (XX.X)	XX (XX.X)	XX (XX.X)
Eyes abnormality	XX (XX.X)	XX (XX.X)	XX (XX.X)
Breathing abnormality	XX (XX.X)	XX (XX.X)	XX (XX.X)
Speech abnormality	XX (XX.X)	XX (XX.X)	XX (XX.X)
Hearing abnormality	XX (XX.X)	XX (XX.X)	XX (XX.X)
Other abnormality	XX (XX.X)	XX (XX.X)	XX (XX.X)

\* at screening

4.3 ANALYSIS OF PRIMARY OUTCOME

Primary objective:

To compare the efficacy of the ACT artemether-lumefantrine versus a multivitamin preparation as defined by the 28-day PCR parasite positivity rate or incidence of confirmed clinical malaria of any species

Primary endpoints:

Composite endpoint

- 1. 28-day PCR Plasmodium positivity rate of any species or
- 2. Proportion of participants with confirmed clinical malaria of any species reported between day 0 and day 28

The main analysis strategy for the primary outcome will be the intention-to-treat (ITT) principle followed by the per protocol (PP) analysis. Thus, we will first analyse the ITT population in which all participants recruited in the trial will be included in the analysis according to the randomisation arm irrespective of what they actually got. These ITT analyses will be followed by the analysis of the per protocol (PP) population in which, participants who did not adhere to the protocol will be excluded from analysis.

The efficacy of the ACT artemether-lumefantrine versus a multivitamin preparation as defined by the 28-day PCR parasite positivity rate or incidence of confirmed clinical malaria analysis in each arm will be summarised using proportions and the 95% confidence intervals. Crude proportions will be calculated with the exact binomial 95% confidence intervals. The risks differences in efficacy between AL and multivitamin will be reported along with the corresponding 95% confidence intervals. The robust standard error will be used to adjust for intracluster correlation of episodes from the same individual. The mixed effects Poisson/negative binomial regression model will be used to model the adjusted incidence rate ratios (IRR). The mixed effects models will take into account the correlation of multiple episodes from same participant.

Tests of significance will be performed at 5% significance level.

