2. SYNOPSIS

Study Title	An open-label individually randomised controlled trial to assess the efficacy of artemether-lumefantrine prophylaxis for malaria among forest goers in Cambodia
ACRONYM	PAL-Cambodia
Trial Design	An open-label randomised trial comparing the ACT artemether-lumefantrine (Coartem) with a multivitamin preparation, evaluating efficacy in preventing malaria among forest goers
Trial Participants	People planning to travel the forest within the next 72 hours in areas at high risk for malaria
Sample size	4400 participant episodes, with half allocated to each study arm
Inclusion Criteria	
 • Male or female, aged between 16 and 65 years • Planning to travel to the forest within the next 72 hours and stay overnight • Written informed consent • Willingness and ability of the participants to comply with the study protocol for the duration of the study
Exclusion Criteria	
 • For females: known pregnancy or breast feeding • Participants who have received artemisinin or a derivative or an artemisinin-containing combination therapy (ACT) within the previous 7 days • History of allergy or known contraindication to artemisinins, lumefantrine or multivitamins • Documented or claimed history of cardiac conduction problems. • Severe vomiting or diarrhoea • Signs/symptoms of clinical malaria (febrile or history of fever in the previous 24hours) confirmed by RDT
Planned Trial Period	12 months (September 2019 – July 2020) enrolment
Primary Objective	To compare the efficacy of the ACT artemether-lumefantrine versus a multivitamin preparation as defined by the 28-day PCR parasite positivity rate and incidence of confirmed clinical malaria of any species.
Secondary Objectives	
 1. To compare the efficacy of the ACT artemether-lumefantrine versus a multivitamin preparation as defined by the 28-day, 56-day and 84-day PCR parasite positivity rate and incidence of confirmed clinical malaria for each species. 2. To quantify the impact of the ACT artemether-lumefantrine as prophylaxis for forest goers on overall malaria transmission using mathematical modelling.

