5.5.3 Exclusion criteria

- For females: known pregnancy or breast feeding
- Participants who have received artemisinin or a derivative or an artemisinin-containing combination therapy (ACT) within the previous 7 days.
- History of allergy or known contraindication to artemisinins, lumefantrine or multivitamins
- Documented or claimed history of cardiac conduction problems
- Severe vomiting or diarrhoea
- Signs/symptoms of clinical malaria (febrile or history of fever in the previous 24 hours) confirmed by RDT.

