6.2.4. Clinical malaria

Participants who are screened and are found to be febrile or have a current history of fever will not be enrolled (as per exclusion criteria) but will be tested for malaria and, if positive, given antimalarial treatment by the village malaria worker or local clinic. All this will be done in accordance with the current national malaria treatment guidelines in Cambodia. Individuals treated for malaria in this way will not be enrolled in the study as per the exclusion criteria.

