6.4. Blood sampling on study enrolment

On study enrolment, immediately before drug administration, blood will be collected for the following:

- Parasite PCR (Up to 1 ml).
- Dried blood spot for capillary blood level of lumefantrine (200 µl)
- Storage for later identification of other causes of fever (2ml).

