6.5. Study drug administration

Overview PAL drug regimens	
ACT arm	Multivitamin arm
Artemether -lumefantrine x 3 days followed by 1 day per week	Multivitamin x 3 days followed by 1 day per week

Participants will be treated with weight-based doses according to the schedule in Appendix 2.

The study drugs will be administered by trained study staff.

If the participant vomits within half an hour after intake of the antimalarial drugs, the dose will be repeated. If vomiting occurs between half and one hour, half of the dose will be repeated. If vomiting occurs more than one hour after drug administration, no repeat dosing will be done. Repeat doses will be recorded on the CRF. If vomiting within 1 hour occurs more than one time, no repeat dosing is allowed. The participant will then be treated at the discretion of the investigator.

The prophylaxis will start with a 3-day course of twice daily AL. This will be followed by 2 doses 8 hours apart on one day per week during the time that the person is travelling in the forest and for 4 weeks after leaving the forest.

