6.6. Follow-up

Participants will be asked to return for a follow-up assessment any time from 28 to 35 days after commencing prophylaxis. This will be regardless of the duration of their visit to the forest or the number of times they visited it in that period. At this assessment, they will be interviewed about how long they spent in the forest, where they went, why, who they travelled with and about risk factors for infection. Brief physical examinations, vital sign and symptom questionnaire will be performed. They will also be asked to report any diagnostic tests and/or treatment for malaria during the preceding 28-35 days.

Blood sampling at follow-up

At each follow-up visit, the following blood will be taken:

All individuals:

- Parasite PCR (Up to 1 ml).

- Dried blood spot for lumefantrine level (0.2 ml)

In those with confirmed clinical malaria at any time point between enrolment and follow-up:

- Dry blood blots (0.4 ml, 3 spots) collected on filter papers for:
 - o Parasite DNA genotyping for genetic markers of antimalarial resistance.
 - o Parasite whole genome sequencing and barcoding to identify geographical origin of parasites and compare genotypes to identify persistent infections.

In individuals who are planning to return again to the forest within the following 28 days after the follow up visit, they will be asked to continue their weekly prophylaxis according to the original treatment allocation on enrolment. They will then be asked to return for a second follow-up visit a further 28 to 35 days later when the above procedure will be repeated. This will be repeated one more time. If the person cannot be followed up within the scheduled period, e.g. because they do not return from the forest in time, then they will be followed up at the first opportunity and this will be recorded in the CRF.

Thus individuals may take prophylaxis continuously for a maximum of 3 periods of 28-35 days in the forest plus 4 weeks after returning totaling 112 days. The choice of study medication for each individual will follow the initial assignment on enrolment throughout the follow-up period.

In those who do not declare an intention to return to the forest within 28 days at any follow-up visit, no further follow-up visits will be offered at that time but they will be asked to complete 4 weeks of prophylaxis following their last day in the forest as post-exposure prophylaxis.

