Individuals who have been enrolled in the study may be enrolled into the study up to two more times during the 12 months study period only if a minimum period of 28 days (4 weeks) has elapsed following their last dose of prophylaxis. Thus they can be enrolled in the study a maximum of three times. If an individual is enrolled again in this way, they will be re-randomised following the same procedure as enrolment.

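### SAP 4.3 gives the day-0 PCR result no role, so for the PCR component no planned analysis shows how much of the effect is prevention of new infection

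*SAP*

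**What the plan says.** The Protocol synopsis describes the trial as "evaluating efficacy in preventing malaria among forest goers". Entry is barred by "Signs/symptoms of clinical malaria (febrile or history of fever in the previous 24 hours) confirmed by RDT" (Protocol 5.5.3). Section 6.2.4 is wider: "Participants who are screened and are found to be febrile or have a current history of fever will not be enrolled". On either wording, a person who carries parasites without fever is eligible.

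Protocol 6.4 provides the baseline sample: "On study enrolment, immediately before drug administration, blood will be collected for the following", with parasite PCR first on the list. Protocol 6.8.1 expects results about 3 to 6 months later, so they cannot affect entry or treatment at the time. Protocol 6.12.1 says that PCR at enrolment and at each follow-up visit is needed for the primary objective, but names no method that uses the enrolment result.

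On treatment, "The prophylaxis will start with a 3-day course of twice daily AL" (Protocol 6.5), while Protocol 6.9.2 states that the comparator has no antimalarial compound.

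For the primary outcome, SAP 4.3 says "we will first analyse the ITT population in which all participants recruited in the trial will be included in the analysis" according to randomised arm, followed by a per-protocol set defined by adherence. It reports proportions, risk differences and adjusted incidence rate ratios. No covariates are stated for the risk difference, and none are named for the rate-ratio model. Table 2 splits results only by follow-up month. Baseline infection appears in SAP 4.4.6 and Table 7, as prevalence by arm, season and risk factor.

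**The concern.** The two arms differ in two ways at once. AL can clear an infection that a participant already carries on day 0, and it can prevent one acquired in the forest. The multivitamin does neither. A carrier on multivitamin who is still positive at day 28 counts as a primary event, and so does a participant newly infected on the trip. The primary contrast adds the two effects together.

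At stake is the reading of a positive result. Part of it could come from clearing infections brought into the trial, yet be reported as protection of forest goers during exposure. The baseline value that helps tell the two apart is already collected. If its use is decided only after results are known, the resulting analysis carries less weight. The concern is mainly with the PCR component: averting illness in a carrier is still prevention of clinical malaria.

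**Working it through.** **The plan's own figure.** Protocol 9.1 and SAP 2.5 give 1,605 episodes per arm for 5% v 3% at 80% power and 5% significance. The two-sided two-proportion formula gives 1,506 uncorrected and 1,605 with continuity correction, so the figure reproduces. The 5% is for *P. falciparum* only and is not split into carried and new infection. The exposure figures in Protocol 9.1 (1 infection per 500 person-nights, 10 nights per episode) give 10/500 = 2% new infection per episode. At that rate, 5% from new infection alone would need 0.05 × 500 = 25 nights.

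**Inputs.** From the documents: 2,200 episodes per arm less 10% loss = 1,980. Assumed, because the documents give no values: 3% new infection on multivitamin; day-0 prevalence of 1%, 3% or 5%; and the percentage of carriers still positive at day 28 on multivitamin/AL, in five pairs. Episodes are treated as independent, with one outcome each; carry-over into Months 2–3 is not modelled.

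**(A) AL prevents nothing and only clears.**

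- Multivitamin positivity = 1 − 0.97 × (1 − prevalence × persistence on multivitamin)
- AL positivity = 1 − 0.97 × (1 − prevalence × persistence on AL)
- Probability of p<0.05 = Φ((d − 1.96·SE₀)/SE₁) plus a negligible or small opposite tail, where d is the difference, SE₀ is pooled and SE₁ unpooled

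Example, 5% prevalence and 40%/5%: multivitamin 1 − 0.97 × 0.98 = 4.94%; AL 1 − 0.97 × 0.9975 = 3.24%; d = 1.70 points; SE₀ = SE₁ = 0.63 points; Φ((1.70 − 1.23)/0.63) = 0.77.

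| Persistence, multivitamin/AL | 1% prevalence | 3% prevalence | 5% prevalence |
|---|---|---|---|
| 20%/5% | 0.06 | 0.12 | 0.23 |
| 40%/20% | 0.06 | 0.16 | 0.32 |
| 40%/5% | 0.09 | 0.40 | 0.77 |
| 80%/20% | 0.17 | 0.76* | 0.98* |
| 80%/5% | 0.24 | 0.93* | >0.99* |

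*Control positivity is 5.3% (3% prevalence) or 6.9% (5% prevalence), above the planned 5%.

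Without the starred cells the ranges are 6–24%, 12–40% and 23–77%. With 1,605 effective episodes per arm they are 6–21%, 10–34% and 20–68%. A test with no effect of either kind would reach p<0.05 5% of the time, so the low ends are close to no effect.

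**(B) AL also prevents 40% of new infections (3.0% v 1.8%).** Clearance share = 1 − 0.012/(multivitamin − AL), with 0.982 replacing 0.97 in the AL formula. In the unstarred cells, clearance supplies 11–38% of the expected difference at 1% prevalence, 27–46% at 3% and 38–59% at 5%.

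**Does any planned analysis already answer this?** The genetics text is mixed:

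- Protocol 6.6 plans to "compare genotypes to identify persistent infections", in samples from confirmed clinical malaria.
- Protocol 6.8.2 first says PCR-positive samples will be processed for genetic analysis, then limits genotyping to confirmed clinical malaria because asymptomatic samples are expected to hold too little material.
- Protocol 6.12.2 mentions typing to identify clones.
- SAP Table 4 sets day-28 positivity against resistance markers.

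None of these plans a comparison of day 0 with day 28 in PCR positives.

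**The case against.** The strongest reply is that the endpoint is defined as positivity, not new infection. The primary objective says so, and Protocol 3.1 gives the purpose of PCR as finding a difference between arms in the prevalence of low-density infection. Clearance may also help to reduce transmission, a further aim in Protocol 3.2. On that view, separating the two effects is an additional question and not a defect in the planned analysis. This stands, and it is why the primary analysis should not change. It does not settle how the result may be described against the stated aim of preventing malaria.

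A reader might also infer more than the documents support:

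- **That baseline prevalence is the only purpose of day-0 PCR.** Protocol 6.12.1 ties it to the primary objective. What is missing is a stated analysis.
- **That the risk difference is declared unadjusted.** SAP 4.3 uses the word crude for the proportions. Day-0 PCR is unspecified as a covariate, not ruled out.
- **That the report would say nothing on the matter.** Table 7 gives day-0 prevalence by arm, and the multivitamin-arm figure roughly caps the points that clearance can add in Month 1. It does not link baseline status to outcome.
- **That clearance alone could almost guarantee significance.** Only the starred cells give that, and they exceed the planned control rate. Any-species positivity could be above the *P. falciparum* figure, so those cells are not impossible, but they should not carry the argument. Scenario (A) is itself a limiting case, since it lets AL clear carried infection yet prevent none during weekly dosing.

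**Conclusion.** The gap is real and limited. SAP 4.3 states no analytic role for day-0 PCR, so for the PCR component nothing planned shows what part of the effect is prevention of new infection. The intention-to-treat contrast remains a valid estimate of the regimen's total effect on the endpoint as defined. A reader might infer that it is biased or that the primary analysis is wrong. Randomisation protects it, and the documents do not support that reading.

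The size cannot be fixed from the documents. At 1% carriage it is probably small; at 5% it could be a large part of the observed difference. Every carriage and persistence figure behind that statement is an assumption. This is a cheap improvement that should be made before results are known.

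**What to change.** In SAP 4.3:

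1. Keep the intention-to-treat composite as primary and describe it as the regimen's total effect.
2. Name day-0 PCR status as a covariate in the adjusted rate-ratio model, for precision and chance imbalance. This alone does not separate clearance from prevention.
3. Pre-specify a supportive estimate with 95% CI, not a pass/fail test, of the composite and of its PCR component in episodes PCR-negative at day 0. Month 1 is the main row. Months 2–3 keep the day-0 classification, because the preceding visit's PCR is measured after randomisation. For people enrolled again, "they will be re-randomised following the same procedure as enrolment" (Protocol 6.6), so each enrolment uses its own day-0 sample. Report this estimate beside any statement about preventing new infection.
4. Describe day-0-positive episodes by arm. They mix persistence with new infection and may be few: 1,980 × 1% ≈ 20 per arm, or 1,980 × 5% = 99.
5. Keep episodes with no day-0 result in the primary analysis and leave them out of item 3.

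The cost is SAP wording and one added analysis on data already collected. The drawback is low power. At 5% prevalence, 1,980 × 0.95 = 1,881 episodes per arm remain. For a 40% reduction:

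- 3.0% v 1.8%: about 56 v 34 events, 67% power, difference 1.2 points (95% CI 0.2 to 2.2).
- 2.0% v 1.2%: about 38 v 23 events, 50% power, difference 0.8 points (95% CI 0.0 to 1.6).

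With 1,605 × 0.95 ≈ 1,525 effective episodes, power is 58% and 42%. A negative PCR means only that no infection was detected, so some carried infection stays in the subset.
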